screening visit. Patients previously receiving ZOF 30 mg or AML 5 mg will continue the same treatment, patients receiving other ACE-i will be switched to ZOF 30 mg, while patients receiving CCBs will receive AML 5 mg. Patients entering this phase in therapy with ZOF 30 mg or AML 5 mg should be in a 1:1 ratio. Assessment period from Visit 2 (Week 0) to Visit 4 (Week 8): patients having uncontrolled BP at Visit 2, will be assigned to the extemporaneous combination of ZOF 30 mg and AML 5 mg. After 4 Weeks \pm 2 days the BP will be assessed again (Visit 3): controlled patients (SBP/DBP ≤ 130/80 mmHg) will continue the same extemporaneous combination, while uncontrolled (SBP/DBP >130/80 mmHg) patients will be up-titrated from extemporaneous combination ZOF/AML 30/5 mg to extemporaneous combination of ZOF/AML 30/10 mg for further 4 weeks \pm 2 days (Visit 4, Week 8). At Visit 2 and Visit 3 patients with SBP/DBP value classified as Grade 3 (SBP \geq 180 or DBP \geq 110 mmHg) hypertension will be withdrawn from the study. *To be enrolled in the study, patients could be in monotherapy with one of the listed CCBs: felodipine, isradipine, lacidipine, lercanidipine, nicardipine, nifedipine, and nisoldipine. The primary endpoint will be assessed before and after assessment period at Week 8, by a paired t-test using the Intention-to-treat (ITT) Statistical population and the Per-Protocol (PP) population. Assumptions All the other continuous secondary/exploratory endpoints will be assessed before (Week 0) and after treatment (at Week 8) by a paired t-test. All secondary/exploratory endpoints related to proportion of patients achieving the BP goal at Week 4 and Week 8 will be analysed descriptively producing also the relative 95% CI to assess if there is a significant difference from Week 0 where all patients were uncontrolled.

[figure not shown]
немъни	Corporate Medical Department		
Identification Number	Version Number	State	Effective date
FORM-000050125	2.0, CURRENT	Effective	08, Jan 2021

Protocol Version 1.0 of 1 23/04/2021

Study Code: : MEIN/20/ZoAm-Hyp/001

A total sample size of 216 patients is required to achieve 90% power at a 5% significance level assuming a difference in mean DBP from baseline (Visit 2) to 8 weeks (Visit 4) of 4 mmHg and a standard deviation (SD) for this difference of 10 mmHg. The mean change in DBP for the null hypothesis is set equal to 2 mmHg.

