### 5.5 Reporting Conventions

The following conventions will be used across all study summaries and analyses, unless otherwise specified in the corresponding section.

- Summary statistics will consist of sample size (n), mean, standard deviation (SD), median, minimum (min), and maximum (max) values for continuous and some ordinal variables; and sample size (n), frequencies, and percentages (%) for categorical and some ordinal variables.
- Statistical tests and confidence intervals (CI) will be two-sided unless otherwise specified; statistical tests will use an alpha threshold of 0.05 and CIs will use 95% confidence unless otherwise specified.
- Mixed Models for Repeated Measures (MMRM) will be fit using the unstructured covariance matrices. In the event of lack of model convergence, other covariance structures may be used.
- P-values will be calculated to three decimal places. P-values less than 0.001 will be presented as "< 0.001."

Unless otherwise specified, descriptive summary tables will be structured with a column for each monotherapy group (ZOF 30 mg or AML 5 mg) or combined treatment group (ZOF/AML 30/5 mg or ZOF/AML 30/10 mg) and overall (All Patients) and will include the total population size for each group in the header. Conversely, inferential summary tables will use only the All Patients column, unless otherwise specified, to prevent overinflation of the type I error rate.

For descriptive summary tables, patients will be classified as either ZOF/AML 30/5 mg or ZOF/AML 30/10 mg such that no patients are counted in both groups. That is, even though patients in the ZOF/AML 30/10 mg group are also exposed to the ZOF/AML 30/5 mg treatment, they will only be included in the ZOF/AML 30/10 mg and All Patients columns within the summary tables, and not within the ZOF/AML 30/5 mg column.

Summary tables will also indicate the number of patients with complete data for each measurement, event, or outcome.

Data listings will be sorted by treatment group, patient, and visit (when applicable).

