### 5.9 Multiple Testing

The current study has a single primary efficacy endpoint. The secondary efficacy endpoints are derived from the primary objective and will be used to support the conclusion of the primary efficacy endpoint, provided that the primary efficacy endpoint is met. Thus, adjustments for multiple testing in the secondary efficacy endpoints will not be applied.

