    - If all logistic MMRM fail to converge, this endpoint will be analyzed as described in section 7.4.2.1 below.
  - *Stratification factor =* presence of diabetes and/or of hypercholesterolemia at baseline

The number (n), proportion (%), and 95% CI of the proportion of patients achieving controlled BP will be presented by visit and treatment subgroup. The odds ratio (OR), 95% CI of the OR, and two-sided p-value for the difference between treatment subgroups in proportion of patients achieving controlled BP will be presented where a p-value of  $\leq$  0.05 indicates a significant difference between groups.

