## 1.1.2 Efficacy

Number	Title	Population	Unique/ Repeat	Supporting Listing	Endpoint
Descriptive	Summary Analyses				
14.2.1.1	Summary and Change from Baseline for Mean Sitting Diastolic Blood Pressure (DBP) by Visit	EFF	Unique	16.2.6	Descriptive Summary
14.2.1.2	Summary and Change from Baseline for Mean Sitting Systolic Blood Pressure (SBP) by Visit	EFF	Repeat	16.2.6	Descriptive Summary
14.2.1.3	Summary and Change from Baseline for Mean Sitting Diastolic Blood Pressure (DBP) by Visit	РР	Repeat	16.2.6	Descriptive Summary
14.2.1.4	Summary and Change from Baseline for Mean Sitting Systolic Blood Pressure (SBP) by Visit	РР	Repeat	16.2.6	Descriptive Summary
Endpoint Ar	nalyses				
14.2.2.1	Summary of Change in Mean Sitting Diastolic Blood Pressure (DBP) from Visit 2 to Visit 4	EFF	Unique	16.2.6	1.1
14.2.2.2	Summary of Change in Mean Sitting Diastolic Blood Pressure (DBP) from Visit 2 to Visit 4	РР	Repeat	16.2.6	1.1 sensitivity
14.2.2.3	Summary of Change in Mean Sitting Diastolic Blood Pressure (DBP) from Visit 2 to Visit 4 Using LOCF	EFF	Repeat	16.2.6	1.1 sensitivity
14.2.2.4	Summary of Change in Mean Sitting Diastolic Blood Pressure (DBP) from Visit 2 to Visit 4 by Study Site	EFF	Repeat	16.2.6	1.1 sensitivity

14.2.2.5	Summary of Change in Mean Sitting Diastolic Blood Pressure (DBP) from Visit 2 to Visit 4 by Gender	EFF	Unique	16.2.4.1, 16.2.6	1.1 sensitivity
14.2.2.6	Summary of Change in Mean Sitting Diastolic Blood Pressure (DBP) from Visit 2 to Visit 4 by Age Group	EFF	Repeat	16.2.4.1 , 16.2.6	1.1 sensitivity
14.2.3.1	Summary of Change in Mean Sitting Systolic Blood Pressure (SBP) from Visit 2 to Visit 4	EFF	Repeat	16.2.6	2.1
14.2.3.2	Summary of Change in Mean Sitting Systolic (SBP) and Diastolic Blood Pressure (DBP) from Visit 3 to Visit 4 for Patients Uncontrolled and Up- Titrated at Visit 3	EFF	Unique	16.2.6	2.2
14.2.3.3	Proportion of Patients Achieving Sitting BP Goal (≤130/80 mmHg) at Visits 2, 3, and 4	FAS, EFF	Unique	16.2.6	2.3
14.2.3.4	Proportion of Patients with 80% - 120% Adherence to Treatment at Visits 2, 3, and 4	FAS, EFF	Repeat	16.2.5.1	2.4
14.2.4.1	Difference in Mean Change for Sitting Systolic (SBP) and Diastolic Blood Pressure (DBP) from Visit 1 to Visits 2, 3, and 4 by Treatment Subgroup	FAS, EFF	Unique	16.2.6	3.1
14.2.4.2	Difference in Mean Change for Sitting Systolic (SBP) and Diastolic Blood Pressure (DBP) from Visit 2 to Visit 3 for Patients with Uncontrolled BP at Visit 3 by Treatment Subgroup	EFF	Repeat	16.2.6	3.2

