#### Table 14.2.4.2

Difference in Mean Change for Sitting Systolic (SBP) and Diastolic Blood Pressure (DBP) from Visit 2 to Visit 3 for Patients with Uncontrolled BP at Visit 3 (Efficacy Population)

			S	BP	D	BP
		-	ZOF/AML [4]	ACE-i/CCB [5]	ZOF/AML [4]	ACE-i/CCB [5]
Visit [1]	Statistic Type [2,3]	Statistic	(N=xx)	(N=xx)	(N=xx)	(N=xx)
Visit 3 CFB	MMRM	n LSM (SE) 95% Cl	xx xx.x (xx.xxx) (xx.x, xx.x)	xx xx.x (xx.xxx) (xx.x, xx.x)	xx xx.x (xx.xxx) (xx.x, xx.x)	xx xx.x (xx.xxx) (xx.x, xx.x)
	v. ACE-i/CCB	LSM Difference (SE) 95% Cl p-value	xx xx.x (xx.xxx) x.xxx		xx xx.x (xx.xxx) x.xxx	

1] CFB = Change from Baseline (Visit 2).

[2] MMRM = Mixed Model Repeated Measures.

[3] Model uses an unstructured covariance matrix; change from baseline for SBP/DBP as the response variable; visit, treatment subgroup, visit\*treatment subgroup interaction, and baseline SBP/DBP as covariates; and a random effect for patient.

[4] ZOF/AML subgroup: Patients who were on ZOF 30 mg or AML 5 mg at Visit 1 (Week -4) and continued on same therapies.

[5] ACE-i/CCB subgroup: Patients who switched to ZOF 30 mg or AML 5 mg from any other ACE-I or CCBs at Visit 1 (Week -4).

Source: Listing 16.2.6

Program Name: XXXX.SAS

Date: DDMMMYYYY

Programming Note:

• If a different covariance structure is used in case of model nonconvergence, footnote 3 should be updated accordingly.

Table 14.2.4.3
Proportion of Patients Achieving Sitting BP Goal (≤ 130/80 mmHg) at Visits 2, 3, and 4 by Treatment Subgroup
(Full Analysis Set and Efficacy Population)

				ZOF/AML [5]	ACE-i/CCB [6]
Therapy Type	Visit	Statistic Type [1,2]	Statistic [3,4]	(N=xx)	(N=xx)
Monotherapy	Visit 2	Logistic MMRM	n/N (Proportion %)	xx/xx (xx.x)	xx/xx (xx.x)
			95% CI	(xx.x, xx.x)	(xx.x, xx.x)
		v. ACE-i/CCB	Odds Ratio	x.xx	
			95% CI	(x.xx, x.xx)	
			p-value	x.xxx	
Combined Therapy	Visit 3	Logistic MMRM	n/N (Proportion %)	xx/xx (xx.x)	xx/xx (xx.x)
			95% CI	(xx.x, xx.x)	(xx.x, xx.x)
		v. ACE-i/CCB	Odds Ratio	x.xx	
			95% CI	(x.xx, x.xx)	
			p-value	x.xxx	
	Visit 4	Logistic MMRM	n/N (Proportion %)	xx/xx (xx.x)	xx/xx (xx.x)
			95% CI	(xx.x, xx.x)	(xx.x, xx.x)
		v. ACE-i/CCB	Odds Ratio	x.xx	
			95% CI	(x.xx, x.xx)	
			p-value	x.xxx	

Note: The Monotherapy analysis (Visit 2) is performed on the Full Analysis Set. The Combined Therapy analysis (Visits 3 and 4) are performed on the Efficacy Population. [1] Logistic MMRM = Logistic Mixed Model Repeated Measures.

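### SAP 7.4 calls up to 23 unadjusted exploratory contrasts between non-randomised subgroups significant at p ≤ 0.05; they should be labelled nominal

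*SAP*

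**What the plan says.** SAP 7.4 defines two subgroups by treatment before the study: patients already on zofenopril 30 mg or amlodipine 5 mg who continued it, and patients who switched from another ACE inhibitor or calcium channel blocker. SAP 4.5 confirms that nothing is randomised.

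- **Decision rule.** SAP 7.4.1 (Endpoints 3.1 and 3.2) and SAP 7.4.2 (Endpoints 3.3 and 3.4) end with the same clause: a two-sided p-value of at most "0.05 indicates a significant difference between groups".
- **General alpha.** SAP 5.5: "statistical tests will use an alpha threshold of 0.05".
- **Multiplicity.** SAP 5.9 deals with the single primary endpoint and then says that "adjustments for multiple testing in the secondary efficacy endpoints will not be applied". It does not mention the exploratory endpoints.
- **Type I error.** SAP 5.5 also says that "inferential summary tables will use only the All Patients column, unless otherwise specified, to prevent overinflation of the type I error rate".
- **Protocol.** For the blood-pressure-goal endpoints the synopsis (Statistical Assumptions) says: "All secondary/exploratory endpoints related to proportion of patients achieving the BP goal at Week 4 and Week 8 will be analysed descriptively", with a 95% CI judged against Week 0. Protocol 12.5.5 plans mixed models for the exploratory endpoints, including a logistic one for the goal, and states no significance rule for them.
- **Shells.** The table for Endpoint 3.3 (14.2.4.3) is titled "Proportion of Patients Achieving Sitting BP Goal (≤ 130/80 mmHg) at Visits 2, 3, and 4 by Treatment Subgroup". SAP 3.2.3 and 7.4.2 define Endpoint 3.3 at Visits 2 and 3 only.

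**The concern.** An exploratory label normally tells the reader to treat p-values as descriptive. Here the SAP goes further and states in advance what a p-value at or below 0.05 will mean. It does so for every visit, blood-pressure parameter and stratum, with no adjustment and no caution.

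Followed literally, the study report would call some continued-versus-switched contrasts significant, including contrasts inside a single hypertension grade or comorbidity stratum. The subgroups differ by prior prescribing, so confounding comes on top of chance. The report would have no pre-specified text telling the reader to discount such a result.

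**Working it through.** The documents give no count of these tests and no family-wise error rate, so there is no planned figure to reproduce.

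**1. Count the p-values in the shells.**

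| Table | Endpoint | Layout | Tests |
|---|---|---|---|
| 14.2.4.1 | 3.1, "from Visit 1 to Visits 2, 3, and 4 by Treatment Subgroup" | SBP and DBP × 3 visits | 6 |
| 14.2.4.2 | 3.2, "from Visit 2 to Visit 3 for Patients with Uncontrolled BP at Visit 3 by Treatment Subgroup" | SBP and DBP × 1 visit | 2 |
| 14.2.4.3 | 3.3 | 3 visits | 3 |
| 14.2.4.4.1 | 3.4 by hypertension grade | 2 strata × 3 visits | 6 |
| 14.2.4.4.2 | 3.4 by diabetes and/or hypercholesterolemia | 2 strata × 3 visits | 6 |

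Total: 6 + 2 + 3 + 6 + 6 = 23, or 22 if Endpoint 3.3 is kept to Visits 2 and 3. This is an upper count. If the logistic models do not converge, SAP 7.4.2.1 falls back on a CI and an odds ratio and names no p-value. If that happened throughout, the 3 + 6 + 6 = 15 goal tests would drop out and 8 would remain.

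**2. Expected chance findings, with no true difference.** Expected number = m × 0.05. For 23 tests it is 1.15, for 22 it is 1.10 and for 8 it is 0.40. Correlation does not change this figure, provided each test holds its 5% level.

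**3. Probability of at least one, if independent.** 1 − 0.95^m:
- m = 23: 1 − 0.307 = 0.693
- m = 22: 0.676
- m = 8: 0.337

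**4. Allow for correlation.** The tests share patients, so they are correlated, and the documents do not say how strongly. With 23 equally correlated normal statistics, the probability of at least one p ≤ 0.05 is:

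| Assumed correlation | Probability |
|---|---|
| 0.3 | 0.58 |
| 0.5 | 0.45 |
| 0.7 | 0.31 |
| 0.8 | 0.24 |

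**5. Simulate the table layout with no true difference.** Two sets of assumptions were used.
- 216 patients split evenly, SBP–DBP correlation 0.3 to 0.7, within-patient correlation 0.5, with t-tests and two-proportion tests standing in for the mixed models: 0.56 to 0.60, and 1.18 to 1.21 significant contrasts per trial. That mean is slightly above 1.15, so the stand-in tests are a little too liberal.
- 290 patients, continued share 20% to 50%, SBP–DBP correlation 0.4 to 0.8, between-visit correlation 0.3 to 0.7, with covariate-adjusted linear and logistic tests: 0.41 to 0.53 over 11 scenarios, and 0.78 to 1.06 contrasts per trial. In sparse strata these tests fall below their 5% level.

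Taken together, the correlated results run from about 0.24 to 0.60.

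**The case against.** Four counter-arguments carry weight.

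- **The endpoints are exploratory.** SAP 3.1.3, 3.2.3 and 7.4 say so, and unadjusted exploratory testing is ordinary practice. Protocol 12.1 also sets two-sided 0.05 as the default for all testing. This stands: no adjustment is needed, and no primary or secondary conclusion depends on these contrasts. It does not justify the significance label.
- **SAP 5.5 is not breached.** A reader might infer that SAP 7.4 contradicts the type I error statement there. The documents do not support that reading. The sentence allows exceptions that are specified elsewhere, and SAP 7.4 is one. The columns that SAP 5.5 describes are also the monotherapy and combined-dose groups, not the continued and switched subgroups.
- **The synopsis does not forbid these tests.** A reader might infer that the 10 goal p-values at Weeks 4 and 8 (5 per visit) violate it. But the synopsis sentence concerns comparison with Week 0, and Protocol 12.5.5 does plan a logistic mixed model with treatment subgroup among its terms. The two protocol statements differ and need reconciling; neither can be taken as overriding the other.
- **The probability is not firm.** A reader might conclude that a false significant finding is about as likely as not. Both simulations are compatible with that, but their ranges (0.41 to 0.53 and 0.56 to 0.60) do not overlap. The equal-correlation figures go down to 0.24. Every figure also presumes no true difference, which non-randomised groups do not guarantee.

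**Conclusion.** The point holds as one of labelling and interpretation. SAP 7.4.1 and 7.4.2 commit the report to calling up to 23 unadjusted contrasts between non-randomised subgroups significant at 0.05, and no text qualifies that.

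The firmest measure of size is 1.15 expected chance findings, given no true difference and tests that hold their level. The probability of at least one is 0.69 under independence and roughly 0.24 to 0.60 under assumed correlations. The count and the probability both fall if the SAP 7.4.2.1 fallback is used.

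The Visit 4 block in Table 14.2.4.3 is a separate mismatch between shell and endpoint, and hardly affects the count (22 instead of 23). The difference between the synopsis and Protocol 12.5.5 is not mentioned in SAP section 10.

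**What to change.** 1. In SAP 7.4.1 and 7.4.2, replace the significance clause with: *p-values for Endpoints 3.1–3.4 are nominal and unadjusted; estimates and 95% CIs are the result and no significance claim will be made.*
2. Footnote Tables 14.2.4.1, 14.2.4.2, 14.2.4.3, 14.2.4.4.1 and 14.2.4.4.2 in the same words. The p-value rows may stay; removing them is optional, since a reader can still see whether a CI excludes no difference.
3. Remove the Visit 4 block from Table 14.2.4.3, or label it as an added descriptive row.
4. Reconcile the synopsis with Protocol 12.5.5 for the blood-pressure-goal endpoints, and record the outcome in SAP section 10.

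The cost is SAP and shell wording, plus a clarification of the protocol. Sample size, data collection and models do not change. The sponsor gives up the word significant for exploratory contrasts.

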### 7.4.2.1 Model Nonconvergence

If the above logistic MMRMs fail to converge, endpoints 3.3 and 3.4 will be analyzed using a 95% binomial confidence interval (CI) and Odds Ratio (OR) for each visit to assess the proportion of patients, by subgroup, who achieve the BP goal. Subgroups will include those described in section 7.4, as well as subgroups for hypertension grade and the presence of diabetes and/or hypercholesterolemia.

### 8 Safety Analyses (Endpoint 2.5)

**Endpoint 2.5**: Safety and tolerability of the monotherapies (ZOF 30 mg and AML 5 mg) after 4 weeks of therapy and of the extemporaneous combination (ZOF 30 mg and AML 5 mg or AML 10 mg) after eight weeks of treatment.

The variables for endpoint 2.5 are laboratory tests, physical examination, vital signs, 12-lead ECG, and incidence of AEs/SAEs, each of which are discussed in the subsections below.

Safety analyses will be performed on the SAF population. Results will be presented as described in section 5.5 unless otherwise specified.

### 8.1 Study Drug Accountability, Exposure, and Adherence

### 8.1.1 Study Medications

Study Medication	Dose	Frequency	Box Details
Zofenopril calcium (ZOF)	30 mg	Once daily	42 tablets (3 blisters of 14 tablets each)
Amlodipine (AML)	5 mg	Once daily	42 tablets (3 blisters of 14 tablets each)
Amlodipine (AML)	10 mg	Once daily	42 tablets (3 blisters of 14 tablets each)

### 8.1.2 Treatment Exposure by Visit

At Visit 1 (Week -4), patients on current treatment with AML 5 mg or approved CCBs (see section 4.2 for list of approved CCBs) are provided with 1 box of AML 5 mg for the 4-week run-in period. Patients on current treatment with ZOF 30 mg or other ACE-i are provided with 1 box of ZOF 30 mg for the 4-week run-in period.

At Visit 2 (Week 0), patients with uncontrolled BP (> 130/80 mmHg) will be provided with 1 box of ZOF 30 and 1 box of AML 5 mg while the following patients will be withdrawn from the study:

- Controlled BP (≤ 130/80 mmHg)
- Grade 3 Hypertension (SBP ≥ 180 mmHg or DBP ≥ 110 mmHg)
- Does not tolerate the treatment
- Treatment adherence below 80% or above 120%

At Visit 3 (Week 4), patients with controlled BP ( $\leq$  130/80 mmHg) will continue with ZOF 30 and AML 5 mg (receiving 1 box of each), patients with uncontrolled BP (> 130/80 mmHg) will be up-titrated to ZOF 30 and AML 10 mg (receiving 1 box of each), and the following patients will be withdrawn from the study:

- Grade 3 Hypertension (SBP ≥ 180 mmHg or DBP ≥ 110 mmHg)
- Does not tolerate the treatment
- Treatment adherence below 80% or above 120%

At Visit 4 (Week 8), the anti-hypertensive effect of the extemporaneous combination (ZOF/AML 30/5 mg and ZOF/AML 30/10 mg) will be evaluated.

### 8.1.3 Drug Accountability

The number of tablets dispensed and returned for each study medication at each visit is recorded in the eCRF and are expected to occur in the amounts detailed below.

Visit 1

- Dispensation:
  - o 42 tablets of ZOF 30 mg, or
  - 42 tablets of AML 5 mg
- Return:
  - Not applicable

Visit 2

- Dispensation:
  - o 42 tablets of ZOF 30 mg and 42 tablets of AML 5 mg
- Return:

- 14±2 tablets of ZOF 30 mg, or
- 14±2 tablets of AML 5mg

#### Visit 3

- Dispensation:
  - 42 tablets of ZOF 30 mg and 42 tablets of AML 5mg, or
  - $\circ$   $\,$  42 tablets of ZOF 30 mg and 42 tablets of AML 10 mg  $\,$
- Return:
  - $\circ$  14±2 tablets of ZOF 30 mg and 14±2 tablets of AML 5 mg

Visit 4

- Dispensation:
  - Not applicable
- Return:
  - 14±2 tablets of ZOF 30 mg and 14±2 tablets of AML 5mg, or
  - 14±2 tablets of ZOF 30 mg and 14±2 tablets of AML 10 mg

The average amount of study medication dispensed and returned will be summarized by medication type and study visit for the SAF Population. All study drug accountability and exposure details, including modified, missed, and interrupted doses, will also presented in by-patient data listings for the SAF population.

### 8.1.4 Treatment Adherence

Investigators should instruct the patient to take the study drug at the same time every day, in the morning. On the days of the patient's visits, the investigator should instruct the patient to not take the study drug at home.

Treatment adherence (eCRF and derived) will be summarized by medication type and study visit for the SAF Population. Adherence details will also be presented in a by-patient data listing for the SAF Population.

#### 8.1.4.1 eCRF-Reported Adherence

Adherence to treatment will be measured through treatment compliance which is 100\*(actual doses taken/planned dose) and will be reported in the eCRF at each visit. A patient who has taken at least 80% and no more than 120% of the required study medication intake since the last visit will be considered as compliant.

#### 8.1.4.2 Derived Adherence

To ensure accuracy of adherence reported in the eCRF, adherence will also be derived directly for each patient at Visits 2, 3, and 4 as outlined below.

Treatment adherence = 100\*(actual dose/planned dose)

Actual dose = tablets dispensed at previous visit – tablets returned at current visit.

• If a subject fails to return IP, then we assume that all IP was used and return amount will be imputed as 0 tablets. This errs on the side of safety, ensuring that subject data is included in the safety analyses and that AEs are classified as treatment-emergent if they occur after dispensation of IP.

Planned dose is 1 dose per day, for the number of days between:

- V1 to V2-1 (monotherapy period approx. 28 days)
  - 1 dose = 1 tablet
- V2 to V3-1 (combined period 30/5 approx. 28 days)
  - 1 dose = 1 tablet of each assigned therapy (2 tablets total per dose)
- V3 to V4-1 (combined period 30/5 or 30/10 approx. 28 days)
  - 1 dose = 1 tablet of each assigned therapy (2 tablets total per dose)

For monotherapy period, adherence will be derived for each individual medication.

For combined therapy periods, adherence will be derived for each individual medication and then those individual adherence values will be averaged to get an overall adherence %.

Example 1:

If a patient has 28 days between V1 to V2-1, and takes 29 ZOF, then adherence is

• ZOF = 100\*(29/28) = 103.57

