### 4.3 Schedule of Assessments

	VISIT 1 / WEEK -4	VISIT 2 / WEEK 0± 2 days	VISIT 3 / WEEK 4± 2 days	VISIT 4 / WEEK 8± 2 days
Informed consent submitted	~			
IWRS f registration	~	1	~	~
Inclusion/exclusion criteria	~			
Medical history	~			
Prior medications	~	5		
Demographic information	~			
Concurrent diseases and medical conditions	~	~	~	1
Monotherapy of ZOF 30 mg or AML 5 mg dispensing a	~			
Extemporaneous combination of ZOF/AML 30/5 mg dispensing		~	√b	
Extemporaneous combination of ZOF/AML 30/10 mg dispensing			10	
Study drug return/accounting (Compliance assessment)		~	~	√
Concomitant medications	1	1	1	1
Urine Pregnancy test	~	1	1	~
Physical examination	~	1	1	~
Vital signs	~	1	1	1
Laboratory tests d	~			~
Blood pressure assessment	~	~	1	✓
ECG	~			~
AE/SAE assessment e	~	1	~	~
BP device provided to patientsh	×			
Patient diary provided to patients g	~	1	1	
Patient diary to be returned by patient if used g			~	~
BP device returned to site i				~

a. Patients on ZOF 30 mg or AML 5 mg will continue the same therapy for 4 weeks. Patients on any other ACE-i will be assigned to monotherapy with ZOF 30 mg and the patients on other CCBs (the allowed CCBs

are: felodipine, isradipine, lacidipine, lercanidipine, nicardipine, nifedipine, and nisoldipine) will be assigned to monotherapy with AML 5 mg

- b. Only patients controlled at Visit 3 will receive ZOF/AML 30/5 mg
- c. Only patients uncontrolled at Visit 3 will receive ZOF/AML 30/10 mg.

d. To ensure patient safety, the patients will be contacted over phone within 24 hours, in case of any abnormality and clinically relevant laboratory test according to the Investigator's judgement at any visit e. The Investigator is expected to also record any AE which was ongoing at the last treatment dose and a follow-up phone call should be made after 2 weeks from the last study visit.

In case AE was ongoing, the Investigator is expected to follow-up until the outcome of the AE has been determined.

- f. IWRS- Interactive Web Response System
- g. The following procedure is applied only in case of COVID-19 restrictions.

h. Patients will be provided with an automatic blood pressure device to be used in case they are not able to go to the study centre due to Covid-19 pandemic situation.

i. The patient will return the device at the last visit at the site

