#### 5.2.4 Visit Windows

It is expected that all visits should occur according to the protocol schedule. All visit data will be tabulated per the evaluation visit as recorded in the Electronic Case Report Form (eCRF), even if the assessment is outside of the visit window. Early termination visits will be presented in both summary tables and data listings, but unscheduled visits will be presented in the data listings only.

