### 7.3.2 Proportion of Patients (Endpoints 2.3 and 2.4)

**Endpoint 2.3**: Monotherapy: Number and proportion of patients achieving the BP goal (sitting BP $\leq$ 130/80 mmHg) at Visit 2 (Week 0). Combination therapy: number and proportion of patients achieving the BP goal (sitting BP $\leq$ 130/80 mmHg) at Visit 3 (Week 4) and Visit 4 (Week 8).

**Endpoint 2.4**: Adherence to the treatments (% of doses taken/doses to be taken) at Visit 2 (Week 0), Visit 3 (Week 4) and Visit 4 (Week 8).

Endpoints 2.3 and 2.4 will be analyzed using a 95% binomial confidence interval (CI) for each visit.

A patient who has taken at least 80% and no more than 120% of the required study medication since the last visit will be considered as compliant. Treatment adherence will be summarized incrementally rather than cumulatively so that changes in adherence over time can be accurately reflected. That is, a patient can be compliant between Visits 2 and 3, but non-compliant between Visits 3 and 4, or vice versa.

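### Counting unreturned study drug as fully taken gives a derived adherence of about 150% whatever the patient took, which distorts the derived version of endpoint 2.4

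*SAP*

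**What the plan says.** SAP 8.1.4.2 defines adherence as 100 × actual dose / planned dose. Actual dose is the number of tablets dispensed at the previous visit minus the number returned at the current one. Planned dose is one tablet of each drug per day. For drug that is not brought back, "then we assume that all IP was used and return amount will be imputed as 0 tablets". The reason given is safety: keeping the patient in the safety analyses and events classed as treatment-emergent. In the combined period each drug's adherence is calculated separately and the two values are averaged.

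SAP 8.1.1 describes every box as "42 tablets (3 blisters of 14 tablets each", and the first interval in 8.1.4.2 is "V1 to V2-1 (monotherapy period approx. 28 days". SAP 8.1.3 lists the Visit 2 dispensing as "42 tablets of ZOF 30 mg and 42 tablets of AML 5 mg" and the expected Visit 2 return as "14±2 tablets of ZOF 30 mg, or" the same count of amlodipine.

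Under SAP 7.3.2, intake of "at least 80% and no more than 120% of the required study medication since the last visit will be considered as compliant", and endpoint 2.4 is analysed with a 95% binomial interval at each visit. Table 14.2.3.4 reports the proportion inside 80–120% in two columns, eCRF-reported and derived. Table 14.3.5 summarises derived adherence as a continuous variable and eCRF adherence by category.

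**The concern.** A tablet count says nothing about a patient who returns no tablets. The rule replaces that unknown with a fixed number set by kit size: 42 tablets supplied for about 28 doses. The result looks like overdosing by half, and it is the same for a patient who took every planned dose and one who took none.

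Three outputs are at stake. Mean derived adherence is pulled upward. Missing information appears as definite non-compliance in one version of a secondary endpoint. In the combined period the artefact can also offset a real shortfall on the other drug. Derived adherence is meant as an accuracy check on the eCRF value, and for non-returners any disagreement between the two could come from the imputation alone.

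**Working it through.** **Reproducing the SAP's own figures.** Example 1: 29/28 = 103.57%. Example 2: (34/34 + 30/34)/2 = 94.12%. Example 3: (10/14 + 16/14)/2 = 92.86%. Expected return: 42 − 28 = 14, and 12 to 16 for intervals of 30 down to 26 days. All agree with the SAP.

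**Intervals.** The schedule allows two days either side, for example "VISIT 3 / WEEK 4± 2 days". If the window is counted from the previous visit, intervals run from 26 to 30 days. If it is counted from a fixed calendar and two visits drift in opposite directions, they run from 24 to 32. SAP 5.2.4 keeps visit data "even if the assessment is outside of the visit window", so longer intervals can also enter the tables.

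**Full non-return (returned = 0).** Adherence = 42 / days:

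| Days | 24 | 26 | 28 | 30 | 32 | 34 | 35 | 36 |
|---|---|---|---|---|---|---|---|---|
| Derived adherence (%) | 175.0 | 161.5 | 150.0 | 140.0 | 131.25 | 123.5 | 120.0 | 116.7 |

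Every value within the windows exceeds 120%. From 35 days on, none does. If both combination boxes are unreturned, the average is the same figure.

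**One of two boxes unreturned, 28 days.** Overall adherence = (150 + x)/2, where x is the other drug's adherence:

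- x = 100 gives 125%: non-compliant.
- x = 50 gives 100%: compliant.
- The result lies within 80–120% for any x from 10 to 90.

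The cut-off moves with the interval. At 26 days the upper limit for x is 240 − 161.5 = 78.5. At 30 days it is 240 − 140 = 100, so a patient at 100% then just passes.

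**Effect on the tables.** The documents give no non-return rate, so this is an illustration. Assume 216 patients, 28-day intervals, full non-return only, and everyone else at 100%.

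| Non-returners | Derived mean (%) | True mean if they took nothing (%) | Derived proportion compliant (%) | True proportion if they took everything (%) |
|---|---|---|---|---|
| 2 (1%) | 100.5 | 99.1 | 99.1 | 100 |
| 11 (5%) | 102.5 | 94.9 | 94.9 | 100 |
| 22 (10%) | 105.1 | 89.8 | 89.8 | 100 |
| 43 (20%) | 110.0 | 80.1 | 80.1 | 100 |

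For 11 non-returners the derived mean is (205 × 100 + 11 × 150)/216 = 102.5% and the derived proportion is 205/216 = 94.9%. That proportion is right if the non-returners took nothing or half, and too low if they took everything. The derived mean is too high in all three cases.

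**The safety reason.** The Safety Population (SAP 5.3.2) requires one dose in the run-in. Treatment-emergent status (SAP 8.2) runs from the first monotherapy dose. Neither uses a tablet count from a later visit.

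**The case against.** Derived adherence is a cross-check. Site staff assess compliance and enter it in the eCRF (Protocol 7.4). The imputation is stated only for the derived value, and both versions are reported. The protocol makes investigators responsible for retrieving supplies (7.2) and asks for empty boxes back (7.4), so non-return may be rare. Losing one combination box means separating a kit dispensed sealed together (Protocol 7.1). Averaging can hide a shortfall without any imputation: Example 3 passes a patient at 71.43% on one drug. Finally, making the values missing is not neutral, because the denominator in Table 14.2.3.4 counts only patients with data.

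Most of this stands and limits the size of the point. On frequency, though, the protocol's COVID-19 provisions (section 8) let patients keep unused drug for later collection or courier return. The formula counts only what is returned at the visit, and neither document says how a late return is treated.

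Three stronger readings are tempting and are not supported:

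- A reader might infer that every non-returner becomes an over-doser. This fails for intervals of 35 days or more, and for single-box loss at 28 days with the other drug at 10–90%.
- A reader might infer that the rule generally reverses the order of good and poor adherers in endpoint 2.4. Full non-returners within the windows count as non-compliant, never as better adherers. A reversal on the binary endpoint needs single-box loss plus averaging. On the continuous summary it concerns patients who took little.
- A reader might infer that non-returners are removed from the Efficacy or Per Protocol Population. The SAP does not say which version of adherence decides membership, and the Per Protocol definition speaks of adherence as reported, which suggests the eCRF value.

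**Conclusion.** The rule is wrong as written for adherence. Within the visit windows a fully unreturned box yields 131% to 175%, and 150% at 28 days, irrespective of intake. It raises the derived means in Table 14.3.5. In the derived column of Table 14.2.3.4 the bias from full non-return is zero or downward. With single-box loss at 28 days the classification can go wrong in either direction.

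These results rest on 42-tablet boxes, one tablet of each drug per day and the ±2-day windows, all taken from the documents. The size across the trial cannot be stated without a non-return rate, and the table of rates above is an assumption. The eCRF-reported column is untouched, and the primary analysis of diastolic pressure does not use adherence as a variable. The point merits correction because the value is known to be artificial and the remedy is cheap.

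**What to change.** Amend SAP 8.1.4.2 so that the all-used assumption applies to exposure and safety only. For derived adherence, set the value to missing when drug is not returned, including the combined value when either box is unreturned. Say whether tablets recovered after the visit may later fill the gap.

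Report the number of non-returners at each visit. In Table 14.2.3.4, also show the proportion with non-returners kept in the denominator and counted as non-compliant, because leaving them out may overstate adherence. In the 11-patient illustration the two figures would be 205/205 = 100% and 205/216 = 94.9%, which shows how much depends on the missing returns.

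The cost is a short SAP edit, some missing derived values and one extra table row. No new data are needed.
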